2.1 Primary Study Endpoints

Specific Aim 1: To estimate the amount of distal femur bone loss in ABL treated osteoporotic patients 15 months post TKA and to compare the bone loss to the bone loss seen in untreated osteoporotic patients 12 months following TKA as reported by the meta-analysis of Prince et.al.³⁹ The limitation of this design is the comparison to a historic control rather than a control arm in this study. The reason this design was chosen is because it would be unethical to not offer treatment to newly diagnosed osteoporotic patients. Therefore, randomization to a control arm is not possible. Furthermore, based on our recent clinical experience we believe the rate of patient choice to refuse treatment will be quite low making recruitment of a non-randomized osteoporotic control arm futile. This reflects a dramatic change in osteoporosis care within orthopedic surgical practice at UW within the past year. Lastly, it is well documented that bone loss will occur in this patient population following TKA as seen in the multiple studies summarized in the Prince article.

Specific Aim 2: To estimate the amount of distal femur bone loss in untreated osteopenic patients 15 months post TKA.

The hypothesis for this aim is that TKA will significantly reduce BMD from baseline to 15 months post surgery in osteopenic patients. To assess this we will conduct a single arm pre-post observational study.

This design was chosen because data in the literature is sparse for BMD levels pre and post TKA in an osteopenic population. Collection of these data could demonstrate significant reduction in BMD following TKA which would lead to the justification of a future prospective study comparing a bone loss mitigating treatment to no treatment (current standard of care) in osteopenic TKA patients.

Specific Aim 3: To compare the amount of bone loss in ABL treated osteoporotic patients to untreated osteopenic patients 15 months following TKA.

The hypothesis for this aim is that the percent decrease from baseline in BMD at 15 months post TKA will be greater in the untreated osteopenic group compared to the treated osteoporotic group.

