It is understood these groups differ at baseline in BMD, but the belief is that after TKA the osteopenic group will become similar to the treated osteoporotic group. This is an exploratory analysis, and as such we may be under-powered to detect a significant effect. If trends in the differences are seen, and osteopenic patients are becoming osteoporotic after TKA, this would further bolster the need for future treatment studies in the osteopenic population.

2.2 Secondary Endpoints/Secondary aims:

- Distal femoral BMD change at the 15% and 60% ROIs
- Femur cortical thickness change at the 15%, 25% and 60% femur ROIs
- Trabecular bone score (TBS) assessment by Texture Research Investigation Platform (TRIP) software change at the 15%, 25% and 60% femur ROIs
- Patient reported outcomes; KOOS JR (knee function score), VR-12 (Veterans RAND 12 Item Health Survey) and Forgotten Joint Survey
- Precision of custom knee regions of interest
- Body composition and lean mass change
- TKA complications, e.g., revision surgery, fracture, etc

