3.0 PRELIMINARY DATA

3.1 Meta-analysis of BMD loss after TKA (See Prince, et. al.)³⁹

This meta-analysis of 14 studies that quantified distal femur BMD change after primary TKA. In the distal femoral supracondylar region, mean BMD losses of 0.09 [0.05,0.13], 0.14 [0.08,0.20], 0.16 [0.10,0.23], and 0.16 [0.12,0.20] g/cm² were reported 3, 6, 12, and 24 months respectively following TKA. This corresponds to a 9.3%, 13.2%, 15.8%, and 15.4% BMD loss at these time points. In summary, there is a rapid and significant ~15% decrease in BMD in the first 6 months after TKA that is sustained to 24 months. Better understanding regarding how pre-/perioperative bone health optimization may affect BMD loss and the subsequent periprosthetic fracture risk of is essential.

3.2 Distal femoral BMD and cortical thickness after TKA compared to the contralateral (non-operated) side (See Thomas et. al, and Blaty, et. al.^{22, 23})

We initially performed measurements in 1 cm ROI increments to define BMD change throughout the femur (Thomas, et. al.). Based upon that data, we developed and evaluated a standardized technique to measure BMD and cortical thickness utilizing existing atypical femur fracture DXA software. We then compared distal femoral BMD and cortical thickness on the TKA side to the contralateral non-operative leg (Blaty, et. al.).²³ Thirty adults (15 M/15 F) age 59-80 years with well-functioning unilateral, primary TKA 2-5 years after surgery had femoral DXA scans performed. BMD and cortical thickness were measured at ROIs located at 15%, 25%, and 60% of the femur length measured from the distal notch. Femur BMD and cortical thickness were compared between limbs (TKA vs. non-operated side) by paired t-test.

BMD was 9.7%, 9.6%, and 3.2% lower ($p < 0.0001$) in the operated femur at the 15%, 25%, and 60% ROI respectively. Evaluation of this cohort by BMD status (normal, osteopenia, osteoporosis) finds distal femur BMD at the 25% ROI to be 12% lower in those with osteopenia and 10.3% lower in those with osteoporosis. Cortical width was lower by 22% ($p < 0.05$) at the 25% ROI on the TKA side but not at the 15 or 60% ROI, likely due to current software limitations. Importantly, at these distal femur ROIs, BMD reproducibility was excellent, despite

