4.2 Participant recruitment and study design

Study participants will be recruited from the UW Total Joint Program at the American Center. Patients expressing interest in study participation at the time of TKA scheduling will subsequently be contacted by a University of Wisconsin Osteoporosis Clinical Research Program (OCRP) study coordinator. Those expressing study interest will be scheduled at the OCRP where, following informed consent, medical history, collection of FRAX risk factors and a screening DXA of the lumbar spine, bilateral femurs/hips and VFA will be performed.

The overall study design is noted in Figure 1. Briefly, study eligibility will be determined by DXA. Those with osteoporosis who elect ABL will make up the treatment group ($n = 29$). An equal number ($n = 29$) will be recruited into the untreated group, i.e., those with osteopenia and no prior fragility fracture.

At screening, all participants will have a physical examination and blood collected for a metabolic panel, 25(OH)D and parathyroid hormone (PTH) measurement with additional sample to bank for potential future testing related to bone metabolism. Additionally, calcium and PRO questionnaires will be collected consisting of the KOOS JR, VR-12, and Forgotten Joint Survey. Subjects will be advised on how to achieve a daily calcium intake of 1,000-1,200 mg through food plus supplements, if needed, and up to 4000 IU of vitamin D₃ daily (as noted below; section 5.1). Subsequently, for those meeting all inclusion/exclusion criteria, ABL will be initiated in the treatment group approximately 3 months (depending on the surgery schedule) prior to their TKA and serum calcium will be assessed after one month of dosing. Subsequently, all subjects will have lumbar spine and bilateral femur DXA repeated within two weeks prior to TKA (± 7 days from the month -0.25 study visit) and again 6 and 15 months post TKA. At these same visits, PRO questionnaires will be administered and blood will be collected for serum banking.

Figure 1: Study Design Schematic

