8.0 POWER CALCULATION AND DATA ANALYSIS PLAN

Specific Aim 1: Sample size justification: Based on previously collected data by this study team, we assume that the osteoporotic patients will have an average (SD) BMD prior to surgery of 1.15 g/cm² (0.2). We hypothesize that on average there will be minimal (< 0.02 g/cm²) bone loss at the 15 month follow-up. With a SD of 0.2, if we have follow-up data on at least 21 osteoporotic patients, we will have 86% power with a two-sided one-sample t-test to conclude that ABL effectively reduces bone loss less than 0.16g/cm². To account for up to 26.5% attrition previously reported in the pivotal ABL study,⁴³ we will enroll and treat 29 osteoporotic patients under going TKA.

Specific Aim 2: Sample size justification: If we assume that there will be a medium to large (Cohen's D = 0.65) effect in the paired differences of BMD from baseline to 15 months post TKA in an osteopenic population, then we will need to recruit 21 patients to have 80% power to detect this effect size. To account for up to 26.5% attrition we will enroll and follow 29 osteopenic patients under going TKA.

Baseline demographic and characteristic variables will be summarized with mean (SD), median (IQR), or N (%) based on the statistical distribution of the variable. The primary comparison will be on the change in distal femoral BMD at 25% ROI of the surgical leg from 3 months pre-TKA to 15 months post-TKA. We will test for a significant difference in the osteoporotic population versus a null hypothesis of -0.16g/cm² with a two-sided one-sample t-test. Similarly, we will test for a significant change in BMD in the osteopenic population versus a null hypothesis of 0g/cm² with a one-sample t-test. Exploratory analyses will compare the change in BMD over time between osteoporotic patients treated with ALB and untreated osteopenic patients with repeated measures ANOVA while controlling for age, sex, and BMI as covariates and treating patient as a random effect. Changes over time in secondary variables

will be estimated by paired differences and tested for significant changes from baseline with paired t-tests. All tests will be conducted at a 5% significance level.

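### Aim 3 is a hypothesis about percent change at month 15, but the planned random-patient repeated measures ANOVA names no month-15 contrast and assumes equal variance of change between all visits (minor: the aim is exploratory)

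*Combined protocol and SAP*

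**What the plan says.** Section 2.1 (Specific Aim 3) states the hypothesis at a single time point and on a percent scale: "the percent decrease from baseline in BMD at 15 months post TKA will be greater in the untreated osteopenic group", compared with the treated osteoporotic group. It then limits the claim: "This is an exploratory analysis, and as such we may be under-powered to detect a significant effect".

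Section 8.0 describes the analysis differently. "Exploratory analyses will compare the change in BMD over time between osteoporotic patients treated with ALB and untreated osteopenic patients", by "repeated measures ANOVA while controlling for age, sex, and BMI as covariates and treating patient as a random effect". It adds: "All tests will be conducted at a 5% significance level".

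Section 8.0 does not say which term is tested, which visits enter, how time is coded, whether a month-15 contrast is taken, or whether percent or absolute change is analysed. It names no covariance structure beyond the patient effect and no sphericity correction.

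DXA is done at screening, and then "all subjects will have lumbar spine and bilateral femur DXA repeated within two weeks prior to TKA" and again at months 6 and 15 (Section 4.2; Table 1). That makes four visits. The baseline is also given in two ways: Section 8.0 measures the primary change from 3 months before TKA, and Section 5.4 measures it from immediately before surgery.

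**The concern.** Two separate things could go wrong.

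- **The test may not match the hypothesis.** The usual product of this model is a group-by-time test over all visits. Its null is that the two groups follow parallel profiles throughout. Aim 3 is about month 15 only. The groups are treated differently before the pre-surgery scan (Section 5.4 requires at least 8 weeks of ABL in one group; the other gets none), so an early difference is possible by design.
- **The standard error may be wrong.** A single random patient effect implies that the variance of change is the same between any two visits. If change across surgery varies more between patients than change between two pre-operative scans, pooling them makes the month-15 confidence limits too narrow.

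At stake is the only comparison between groups within the trial. Section 2.1 says trends in it would support future treatment studies in osteopenia.

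**Working it through.** **The plan's own figures.** No power or error rate is given for Aim 3 beyond the 5% level. The figures for the other aims reproduce:
- Aim 1: difference 0.16 - 0.02 = 0.14 g/cm², SD 0.2, n = 21. Noncentrality 0.14/(0.2/√21) = 3.21 on 20 df gives 86.2% power (stated 86%).
- Aim 2: d = 0.65, n = 21 gives 80.9% (stated 80%).
- Attrition: 21/(1 - 0.265) = 28.6, so 29 per group, as stated.

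**Hand check of the variance assumption.** In a balanced random-patient ANOVA, twice the within-patient mean square estimates the average of the variances of change over all pairs of visits. The model applies that average to every contrast.

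Assumed SDs of change in g/cm² (not in the documents, except that 0.20 is the plan's working SD):
- screening to pre-surgery 0.02
- screening to month 6, and pre-surgery to month 6: 0.18
- screening to month 15, and pre-surgery to month 15: 0.20
- month 6 to month 15: 0.09

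Average variance = (0.0004 + 0.0324 + 0.04 + 0.0324 + 0.04 + 0.0081)/6 = 0.1533/6 = 0.0256, against a true 0.04 for month-15 change.

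With n = 21 per group:
- SE from the model = √(2 × 0.0256/21) = 0.049
- correct SE = √(2 × 0.04/21) = 0.062
- ratio = √(0.0256/0.04) = 0.80

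The nominal 5% test then rejects with probability P(|Z| > 1.96 × 0.80 = 1.57), about 12%.

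**Simulation with no group difference at any visit.** There were 20,000 trials per scenario with 21 per group (four-visit null scenarios also at 29), complete normal data, and the same covariance in both groups. Age, sex and BMI do not vary over time, so they do not alter the within-patient test in complete data. The contrast is month 15 minus the first visit.

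| Visits and variances of change | Month-15 contrast | Group-by-time F |
|---|---|---|
| Four visits, equal variances | 5.0-5.1% | 5.1-5.2% |
| Two visits | 5.0% | 5.0% |
| Three visits, unequal | 6.6-12.7% | 5.3-6.9% |
| Four visits, unequal | 8.0-17.4% | 6.1-9.3% |

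The unequal four-visit cases assumed SDs of change of 0.02-0.10 before surgery, 0.10-0.20 at month 6 and 0.10-0.20 at month 15, plus random-walk and AR(1) patterns. Another set of assumed variances gave about 6-12% for the contrast and 7-10% for the F test. Taken together, the four-visit ranges are roughly 6-17% and 6-10%. If the contrast is taken from the pre-surgery visit, the same four-visit unequal runs give 4.4-14.5%, so the size also depends on the baseline.

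**Simulation with a difference only before surgery or only at month 6, and equal change from screening to month 15.** The group-by-time F test rejected 11-34% of the time for a 0.05 g/cm² difference and 33-98% for 0.10. Under equal variances the figures were 11-34% and 33-93%, so this needs no unequal-variance assumption. Further assumed variances gave 16-99% for 0.05 at month 6 only.

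A two-sample t-test on change from screening to month 15 held 4.6-5.5% in every scenario.

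**The baseline matters too.** Where only the pre-surgery visit differed by 0.05 and variances were equal, the contrast from pre-surgery to month 15 rejected 13-36%, while the contrast from screening stayed at 5%. The two baselines in Sections 5.4 and 8.0 therefore pose different questions.

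**The case against.** The strongest reply is that Section 8.0 is underspecified rather than wrong. It names neither the visits nor the term tested. With only baseline and month 15 in the model, or with equal variances of change, the error rate is 5%. The aim is exploratory, compares non-randomised groups acknowledged to differ at baseline, and supports no confirmatory claim. All of this stands, and it limits the weight of the point.

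Four stronger readings that a reader might infer are not supported:
- **That the plan rejects a true null at 2 to 3 times the 5% level.** That size can arise for a month-15 contrast with pooled error under some assumed variances. The plan never says it will compute that contrast, and the F test stayed below twice 5% when no visit differed.
- **That the protocol's data disprove equal variances.** The 0.85-1.3% in Section 3.2 is measurement reproducibility, not observed change over about 3 months. The SD of 0.2 is a planning value that Section 8.0 introduces for pre-surgery BMD and reuses for follow-up. Smaller pre-operative variance of change is plausible, but it is an inference.
- **That an early-only difference is expected.** For untreated patients Section 3.1 reports that "there is a rapid and significant ~15% decrease in BMD in the first 6 months after TKA that is sustained to 24 months", and Section 5.2 has ABL given daily for 18 months. A difference that disappears by month 15 is hypothetical.
- **That rejection for an earlier difference is a false positive.** It is a correct rejection of the F test's own null. The fault is that this null is not Aim 3's.

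What the reply does not remove is that the stated hypothesis and the stated method differ. Exploratory status excuses low power, but it does not make a p-value for a different question answer this one.

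**Conclusion.** The point holds as a mismatch between hypothesis and method, and it is minor. Aim 3 concerns percent change at month 15. The plan offers a model of change over time with no month-15 contrast and a restrictive covariance. If all visits enter, the overall test can be significant for reasons unrelated to month 15.

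If variances of change are unequal, the model's month-15 limits can be too narrow: under the assumptions shown, a true null is rejected roughly 6-17% of the time by the contrast and 6-10% by the F test, instead of 5%. These figures rest on assumed variances and correlations, complete normal data and four visits. The imputation planned in Section 8.0 was not modelled. Aims 1 and 2 use one-sample t-tests and are unaffected.

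**What to change.** In Section 8.0, replace the Aim 3 sentence so that the hypothesis is tested by the group difference in change from baseline to month 15. Either of these would do:
- a linear model on month-15 percent change with group, age, sex and BMI, which needs no covariance structure; or
- a mixed model for repeated measures with the same covariates, visit as a category, group-by-visit terms, an unstructured within-patient covariance and Kenward-Roger degrees of freedom.

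Choose one in advance and report the month-15 group contrast with its 95% CI. State that the overall group-by-time test is descriptive and does not decide Aim 3. State the scale (percent, as in Section 2.1). Name a single baseline visit, reconciling Section 8.0 (3 months before TKA) with Section 5.4 (immediately before surgery).

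The cost is wording only; data and visits are unchanged. The month-15 interval may be somewhat wider than the random-patient model would show: in the worked example the SE rises by a factor of 1/0.80 = 1.25. The exploratory result may therefore look less favourable.

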5.4 Pre-TKA Study Visit

All subjects will have TKA surgery approximately 3 months after their screening DXA visit, depending on the surgery schedule. The osteopenic group must have screening data at least 4 weeks prior to but not more than 6 months before this visit. The osteoporotic group must have received at least 8 weeks of ABL prior to this visit. Such variability is acceptable as this reflects clinical care and the primary comparison is BMD change from immediately prior to surgery to 15 months after TKA. As the usual wait time for surgery scheduling in our facility is ~2 months, this should not present a major impediment to study recruitment. The week prior to their scheduled TKA surgery all subjects will return to the OCRP and have repeat lumbar spine, bilateral femur/hip (including distal femur), forearm, PA & bilateral knee and total body DXA measurement, BIS, blood collection and adverse event assessment. Calcium and vitamin D₃ will be dispensed as appropriate. Additionally, subjects will be questioned regarding adverse events, falls and fractures; a physical exam or VFA may be performed if indicated per an investigator. If surgery is delayed for any reason, the study physician will determine if study continuation is appropriate and adjust the study visit timeline as necessary, this may include repeating laboratory tests and/or DXA exams.

5.5 6-month

All subjects will return to the OCRP for DXA (lumbar spine, bilateral femur/hip (including distal femur), forearm, total body, PA & lateral knee), BIS measurement and blood collection. Subjects will be questioned regarding adverse events, falls and fractures and PRO questionnaires will be completed; a physical exam or VFA may be performed if indicated per an investigator. Calcium and vitamin D will be dispensed as needed.

5.6. 15-month

All subjects will return to the OCRP for DXA (lumbar spine, bilateral femur/hip (including distal femur), forearm, PA & lateral knee and total body), BIS measurement and blood collection. Subjects will be questioned regarding adverse events, falls and fractures and PRO questionnaires will be completed; a physical exam or VFA may be performed if indicated per an investigator.

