5.9 Subject Discontinuation or Early Termination

Subjects will be informed that they have the right to withdraw from study participation at any time for any reason without prejudice to their medical care. The Investigator must withdraw subjects for the following reasons:

- Hypercalcemia (two consecutive measurements of > 10.5 mg/dL) that persists despite ABL dose reduction.
- Severe hypersensitivity to abaloparatide
- Inability to complete study procedures
- Lost to follow-up

The Investigator may withdraw subjects for any of the following reasons:

- Serious adverse events
- Non-compliance or protocol violations
- Incident vertebral or non-vertebral fragility fracture
- Other situations that may harm subjects or compromise study integrity

All subjects withdrawn prior to completing the study should be encouraged to have study procedures scheduled for the Month 15 visit as deemed appropriate by the PI. Subjects who discontinue or are withdrawn from the study will not be replaced.

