If a subject drops out or is lost to follow-up prior to data collection at time of surgery, they will be completely removed from the study and a new participant will take their place. If a subject drops out or is loss to follow-up after surgery, they will remain in the study and we will implement various data imputation methods like last observation carried forward (LOCF) and linear prediction imputation.

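### Patients who leave before surgery are removed and replaced under Section 8.0 but not replaced under Section 5.9, and removal can drop ABL-exposed early leavers from the denominators

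*Combined protocol and SAP*

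**What the plan says.** The dropout paragraph of Section 8.0 separates losses before and after surgery. For a subject who drops out or is lost before data collection at surgery, "they will be completely removed from the study and a new participant will take their place". Later losses stay in and are imputed.

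Section 5.9 lists mandatory withdrawals, among them "Lost to follow-up" and hypercalcemia that persists after dose reduction. It then says, with no limit on timing: "Subjects who discontinue or are withdrawn from the study will not be replaced". It also says: "All subjects withdrawn prior to completing the study should be encouraged to have study procedures scheduled for the Month 15 visit".

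Four other statements bear on this:

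- Section 5.2 starts ABL 12 weeks before the scheduled TKA.
- Section 5.4 sets a minimum exposure: "The osteoporotic group must have received at least 8 weeks of ABL prior to this visit".
- Section 8.0 sizes Aim 1 on the basis that "we will enroll and treat 29 osteoporotic patients under going TKA".
- The start of the primary change differs by section. Section 8.0 measures it "from 3 months pre-TKA to 15 months post-TKA", while Section 5.4 says "the primary comparison is BMD change from immediately prior to surgery to 15 months after TKA".

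No safety or analysis population is defined.

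**The concern.** For a patient lost between the first ABL dose and surgery, one section calls for a substitute and the other forbids it. One removes the patient entirely and the other asks for the Month 15 procedures. The number who will start ABL is therefore not settled in advance, and neither is the denominator for attrition.

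This is not replacement of screening failures. The weeks before surgery are when early intolerance would appear: serum calcium is checked about four weeks after the first dose, and Section 5.3 can lead to a mandatory stop. Aim 1 compares a single arm with a fixed historical value, so no concurrent control undergoes the same selection. If early leavers are taken out of the record, early ABL discontinuation is understated and the observed attrition is no longer comparable with the 26.5% borrowed from the pivotal ABL study.

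**Working it through.** **The plan's own figures.** Section 8.0 gives, for Aim 1, an expected loss of 0.02 g/cm² (the plan says less than this) against a null of 0.16, SD 0.2, 21 evaluable patients and a two-sided 5% one-sample t-test. The difference is 0.16 − 0.02 = 0.14, and noncentral-t power is 86.2% (stated: 86%). Enrolment is 21 / (1 − 0.265) = 28.6, rounded up to 29. Both reproduce.

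**Assumed pre-surgery loss, p.** The documents give none. Assume that the 26.5% covers all 18 months of ABL, of which about 3 precede surgery.

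- Constant hazard: p = 1 − (1 − 0.265)^(3/18) = 5.0%.
- Half of the attrition early: p = 0.265 / 2 = 13.25%, shown as 13.3%.

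**What each rule implies (expected numbers).**

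| Quantity | Formula | p = 5.0% | p = 13.3% |
|---|---|---|---|
| 8.0: ABL starters | 29 / (1 − p) | 30.5 | 33.4 |
| 8.0: starters removed | starters − 29 | 1.5 | 4.4 |
| 8.0: attrition counted on the 29 at surgery | (0.265 − p) / (1 − p) | 22.6% | 15.3% |
| 8.0: evaluable | 29 × (1 − that attrition) | 22.4 | 24.6 |
| 5.9: ABL starters | fixed | 29 | 29 |
| 5.9: reach surgery | 29 × (1 − p) | 27.5 | 25.2 |
| 5.9: evaluable | 29 × 0.735 | 21.3 | 21.3 |

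Both rules leave at least the 21 evaluable patients required. This depends on 26.5% being the total. If 26.5% were lost after surgery as well, Section 8.0 would still give 29 × 0.735 = 21.3. Section 5.9 would give 29 × 0.95 × 0.735 = 20.2 or 29 × 0.8675 × 0.735 = 18.5, with power of about 84% or 80% (n = 20 or 18).

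**Effect on the Aim 1 mean.** Add the removed starters back and suppose that all have TKA. If they lose 0.02 g/cm² like the rest, nothing changes. As an upper bound, let each lose the full 0.16:

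- p = 5.0%: (22.4 × 0.02 + 1.5 × 0.16) / 24.0 = 0.029, a shift of 0.009.
- p = 13.3%: (24.6 × 0.02 + 4.4 × 0.16) / 29.0 = 0.041, a shift of 0.021.

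Power on those enlarged groups is 86.7% (n = 24.0, difference 0.131) and 86.9% (n = 29.0, difference 0.119) with SD 0.2. Allowing for the mixture of two means, the SDs are 0.203 and 0.206 and power is 85.7% and 84.8%.

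**Hypercalcemia stops.** The Section 5.3 sequence ends between 4 weeks − 5 days + 1 + 1 weeks = 5.3 weeks and 4 weeks + 5 days + 2 + 2 weeks = 8.7 weeks after the first dose, plus the prompt retest. The pre-TKA visit is allowed from week 8, so most but not all such stops precede it. The stop is an investigator withdrawal under Section 5.9, and the text does not say whether it also counts as dropping out under Section 8.0.

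**The case against.** The best defence is that Section 8.0 is specific and Section 5.9 general: replace before surgery, and do not replace after it. That is a natural reading, although neither section states it, and it would settle who is replaced. It does not settle removal. Complete removal still applies to patients who have taken the drug, and it still clashes with the encouragement to attend at Month 15.

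Several other objections stand and limit the point:

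- Much of the selection for early tolerance comes from the 8-week ABL minimum in Section 5.4. A patient who stops ABL early fails that requirement whatever Section 8.0 says, so the selection cannot be charged to the dropout paragraph alone.
- Aim 1 concerns bone loss after TKA. Replacing someone who never has the operation is reasonable. For BMD, only those who leave or stop ABL before surgery and still have TKA are at issue, and the documents give no count of them.
- A reader might infer that adverse-event data on early leavers are discarded. The documents do not say so. Sections 5.2 to 5.4 collect adverse events before surgery, and the removal sentence stands beside the BMD imputation rules. What can be said is that, with no safety population defined, nothing guarantees that these patients are counted.

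**Conclusion.** The two sections conflict for patients who leave before surgery, and the removal rule is a fault even if Section 8.0 is taken to prevail. It drops ABL-exposed early leavers from the attrition denominator, could drop them from the adverse-event denominator and, jointly with Section 5.4, selects the Aim 1 group for early tolerance.

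The size is modest and rests on the assumed 5.0% to 13.3% pre-surgery loss: roughly 1.5 to 4.4 starters unaccounted for, and attrition that looks like 22.6% to 15.3% when it is 26.5%. The effect on the Aim 1 mean is unknown and probably small, 0 to about 0.02 g/cm² against a planned difference of 0.14. The top of that range needs every removed starter to have TKA and to lose as much as untreated patients.

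A reader might infer that Aim 1 is underpowered or that its conclusion could reverse. With 26.5% as total attrition, as the plan uses it, neither follows: the 86% stands under both rules. The point should be corrected before enrolment for the sake of denominators and accountability.

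**What to change.** Put one rule in both Section 8.0 and Section 5.9:

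> A subject who leaves before surgery, for any reason including investigator withdrawal, will be replaced for the BMD analysis only if TKA is not performed. Every subject who takes at least one ABL dose stays in the study record. Adverse events, ABL discontinuations and attrition are reported as number and percent of all ABL starters, with the numbers stopping before surgery (with reason) and the numbers replaced. A subject who stops ABL before the 8-week minimum but has TKA is invited to the post-TKA DXA visits, is not in the primary Aim 1 analysis, and is included in a sensitivity analysis of Aim 1 over all ABL starters who had TKA. That sensitivity analysis uses the last DXA before the first ABL dose as baseline for everyone. If the primary analysis uses the pre-surgery baseline, the primary population is also shown with the pre-ABL baseline, so that only the population differs.

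The last sentence is needed because Sections 5.4 and 8.0 disagree on the baseline. That disagreement should be settled separately.

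The cost is a rewritten paragraph, a matching one in Section 5.9 and a short accountability table. Screening DXA and pre-surgery adverse events are already collected. A few DXA visits are added, most of them already encouraged by Section 5.9. The sensitivity analysis may show a smaller effect than the primary one.
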